2.2.1 Treatment Duration

Each cycle is 14 days, with Days 6, 7, 13, and 14 being rest days for AM0010. FOLFOX will be administered on Day 1 of each cycle. Patients randomized to the investigational combination treatment (AM0010 plus FOLFOX) ARM 1, after completion of up to 12 cycles of combination chemotherapy or if experiencing chemotherapy intolerance (as defined as Grade 3 or 4 non-hematologic toxicity that has not resolved to baseline in 28 days or Grade 4 hematologic toxicity that has not resolved to baseline in 28 days) may continue to receive maintenance AM0010 if the patient continues to receive clinical benefit (CR, PR, or SD). Patients may receive FOLFOX on both study arms for up to 12 cycles or 24 weeks. Patients will be treated until tumor progression by RECIST v.1.1.

Patients may continue on treatment until they experience progressive disease, unacceptable toxicity, require palliative radiotherapy, withdraw consent, or their physician feels it is no longer in their best interest to continue on study treatments.

To mitigate the chance of detecting false-progression (ie, pseudoprogression) early in the course of treatment on ARM 1 with AM0010 in combination with FOLFOX, patients whose scans show radiographic progression in the absence of clinical deterioration including worsening ECOG PS as assessed by the Investigator may remain on study treatments and should have an additional scan 4

weeks (± 3 days) later as outlined in Section 8.1.1. If this subsequent scan shows disease progression, the patient will be discontinued from study treatments.

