ARM 1: AM0010 (5 µg/kg) subcutaneous (SQ) dosed on Days 1–5 (with rest on Days 6 and 7) and Days 8–12 SQ (with rest on Days 13 and 14) plus a FOLFOX regimen (a 2-hour infusion of *dl*-LV 400 mg/m² and oxaliplatin 85 mg/m² followed by bolus 5-FU 400 mg/m² and a 46- to 48-hour infusion of 5-FU 2400 mg/m²) initiated on Day 1 of a 14-day cycle for up to 12 cycles or until disease progression by RECIST v.1.1.

While receiving FOLFOX during Cycles 1–12, AM0010 at 5 µg/kg will be administered as 1 of 2 fixed doses, either 0.4 mg for patients weighing ≤80 kg or 0.8 mg for patients weighing >80 kg.

Patients in ARM 1 may continue on maintenance cycles with AM0010 (as shown below). After discontinuation of FOLFOX in the absence of tumor progression (ie, completion of the planned 12 cycles or unacceptable FOLFOX related toxicity), AM0010 at 10 µg/kg will be administered as 1 of 2 fixed doses, either 0.8 mg for patients weighing ≤80 kg or 1.6 mg for patients weighing >80 kg.

ARM 1: AM0010 plus FOLFOX, for up to 12 cycles or until disease progression by RECIST v.1.1.

ARM 1: AM0010 plus FOLFOX

[figure not shown]

ARM 1 in the absence of tumor progression may continue maintenance with AM0010 alone at either 0.4 mg for patients weighing ≤ 80 kg or 0.8 mg for patients weighing > 80 kg after completion of FOLFOX or FOLFOX intolerance

ARM 2: FOLFOX alone, initiated on Day 1 of a 14-day cycle, for up to 12 cycles or until disease progression by RECIST v.1.1.

**Study Design
(continued)**

ARM 2: FOLFOX Alone

[figure not shown]

Crossover of patients from the FOLFOX-only treatment arm into the FOLFOX plus AM0010 treatment arm is not permitted.

Patients randomized to the investigational combination treatment (AM0010 plus FOLFOX) ARM 1, after completion of up to 12 cycles of combination chemotherapy or if experiencing chemotherapy intolerance (as defined as Grade 3 or 4 non-hematologic toxicity that does not resolve to baseline in 28 days with standard of care or hematologic Grade 4 toxicity that does not resolve to baseline in 28 days), may continue to receive maintenance AM0010 if the patient continues to receive clinical benefit (CR, PR, SD).

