2.2 Study Design

This is a randomized, open label, global Phase 3 Study of AM0010 in combination with FOLFOX compared with FOLFOX alone as second-line therapy in patients with advanced metastatic pancreatic cancer that has progressed during or following a first-line gemcitabine-containing regimen.

Approximately 566 patients will be randomized. Two interim analyses are planned. The first interim analysis will be performed when at least 60 randomized patients have had the opportunity to receive 4 months of therapy from the date of Randomization. Based on the first interim analysis, the Data Monitoring Committee (DMC) will review the PK exposure-safety and PK exposure-efficacy on the composite aggregate data for a Go/No-Go decision to enroll the entire Phase 3 study. The enrollment will continue during the analysis. The second interim analysis will occur when approximately 276 deaths (70% of total 393 deaths needed for final analysis) have occurred. Based on the second interim analysis, the DMC will recommend modifying, continuing the trial as planned, or discontinuing the trial.

Patients will be randomized in a 1:1 ratio to AM0010 combined with FOLFOX or FOLFOX alone.

The randomization will be stratified by 2 stratification factors:

- Prior single-agent gemcitabine therapy versus gemcitabine/nab-paclitaxel therapy
- North America versus Europe versus APAC.

Treatment Arms:

[figure not shown]
ARM 1: AM0010 (5 µg/kg) SQ dosed on Days 1–5 (with rest on Days 6 and 7) and Days 8-12 SQ (with rest on Days 13 and 14) plus FOLFOX (*dl*-LV 400 mg/m² and oxaliplatin 85 mg/m² followed by bolus 5-FU 400 mg/m² and a 46- to 48-hour infusion of 5-FU 2400 mg/m²) initiated on Day 1 of a 14-day cycle, for up to 12 cycles or until disease progression by RECIST v.1.1.

While receiving FOLFOX during Cycles 1–12, AM0010 at 5 µg/kg will be administered as 1 of 2 fixed doses, either 0.4 mg for patients weighing ≤80 kg or 0.8 mg for patients weighing >80 kg.

Patients in ARM 1 may continue on maintenance cycles with AM0010 (as shown below). After discontinuation of FOLFOX in the absence of tumor progression (ie, completion of the planned 12 cycles or unacceptable FOLFOX related toxicity), AM0010 at 10 µg/kg will be administered as 1 of 2 fixed doses, either 0.8 mg patients weighing ≤80 kg or 1.6 mg for patients weighing >80 kg.

ARM 1: AM0010 plus FOLFOX, for up to 12 cycles or until disease progression by RECIST v.1.1.

Figure 4: ARM 1: AM0010 + FOLFOX

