4.0 STUDY TREATMENT DISCONTINUATION AND STUDY DISCONTINUATION

4.1 Study Treatments Discontinuation

AM0010 or any of the components of FOLFOX can be discontinued for any of the following reasons.

- Adverse events
- Pregnancy
- Investigator decision to discontinue the patient from the components of the study treatments, in consultation with Lilly Medical Monitor
- Clinical disease progression
- Radiographic disease progression by RECIST v.1.1
- Intercurrent illness that would, in the judgment of the Investigator, affect assessments of clinical status to a significant degree
- Initiation of new anti-neoplastic therapy in the absence of tumor progression
- Patient request to discontinue study treatments
- Withdrawal of consent
- Death
- Discontinuation of the study at the request of Lilly, a regulatory agency, or an Institutional Review Board or Independent Ethics Committee (IRB/IEC)
- Poor or non-compliance with study procedures
- Major protocol violation
- Loss to follow-up

Should this occur, the corresponding study drugs completion CRF should be entered to document the reason for discontinuation. In addition, the patient should continue with the rest of the treatment regimen and the study-related procedures per the protocol.

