5.1 Treatment Administration

5.1.1 AM0010

AM0010 is provided as a sterile, clear solution formulated at a concentration of 2 mg/mL and 4 mg/mL.

The AM0010 drug product is stored at the pharmacy at 2°C to 8°C. Patients will store their AM0010 in their refrigerator (2°C to 8°C).

While receiving FOLFOX during Cycles 1–12, AM0010 5 µg/kg will be administered as 1 of 2 fixed doses, either 0.4 mg for patients weighing ≤80 kg or 0.8 mg for patients weighing >80 kg.

AM0010 will be administered as a fixed dose, bracketed in 2 weight groups. Ongoing PK analysis has shown that the apparent clearance is proportional to weight supporting a weight-based dosing.

The rationale for dosing at a flat rate with a cutoff at 80 kg is based on safety and on the PK/Pharmacodynamic relationship. More specifically, immune activation with AM0010 requires a serum trough of at least 1 ng/mL. This trough level is reached with actual doses of 2.5 µg/kg and higher. The MTD of AM0010 is 20 µg/kg. Following the bracketed fixed dosing regimen, all patients will receive between 5 and 10 µg/kg AM0010. This dose range correlated with a survival benefit in a Phase 1b study with AM0010 + FOLFOX in PDAC patients.

The effects of overdose with AM0010 and an antidote to overdose with AM0010 are unknown. Non-human primates have been exposed to 5-10 times the expected serum concentration in humans without acute adverse reactions.

For any subject experiencing AM0010 overdose, observation for any symptomatic side effects should be instituted and vital signs and biochemical and hematologic parameters should be followed closely

(consistent with the protocol or more frequently, as needed). Appropriate supportive management to mitigate adverse effects should be initiated.

After discontinuation of FOLFOX (ie, completion of the planned 12 cycles or unacceptable FOLFOX-related toxicity), the AM0010 dose at the 10- $\mu\text{g}/\text{kg}$ dose level will be administered as 1 of 2 fixed doses (ie, either 0.8 mg in 0.2 mL for body weight ≤ 80 kg or 1.6 mg in 0.4 mL for body weight > 80 kg), based on the patient's weight during the course of the study.

In 144 patients who received AM0010 monotherapy, the MTD was determined at 20 $\mu\text{g}/\text{kg}$ (Naing et al., 2016). Pharmacodynamic analysis indicates immune activation at 10 $\mu\text{g}/\text{kg}$ in a monotherapy setting.

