6.3 ARM 1 Subsequent Cycles AFTER Discontinuation of FOLFOX

6.3.1 ARM 1 (Investigational) Maintenance Cycles after Termination of FOLFOX (Every 28 Days)

In the absence of tumor progression, after completion of up to 12 planned cycles of FOLFOX or discontinuation of FOLFOX due to toxicity, patients assigned to ARM 1 may continue on AM0010 monotherapy at 10 µg/kg (either 0.8 mg for patients weighing ≤80 kg or 1.6 mg for patients weighing >80 kg, administered 5 days on and 2 days off).

Dose reductions in maintenance are the same as in combination at 80% and 60% by altering dose schedule. The 80% dose is administered 4 days on and 3 days off and the 60% dose is administered 3 days on and 4 days off.

The numbering of cycles during maintenance treatment in ARM 1 will follow the convention of “Maintenance Cycles” with Maintenance C1D1 beginning after discontinuation of FOLFOX and start of monotherapy AM0010 as described above. Each Maintenance Cycle will be 28 days/4 weeks in duration.

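### The toxicity route into AM0010 maintenance after an early FOLFOX stop is worded inconsistently, so the same Arm 1 patient can qualify under Section 6.3.1 and not under Section 2.2.1

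*Protocol*

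**What the plan says.** All versions agree that maintenance is open to Arm 1 patients without progression who have finished the planned FOLFOX cycles. They differ on the patient who stops FOLFOX early.

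- **Graded 28-day definition.** Protocol 2.2.1 opens maintenance for "chemotherapy intolerance (as defined as Grade 3 or 4 non-hematologic toxicity that has not resolved to baseline in 28 days", or for Grade 4 hematologic toxicity lasting as long. SAP 6.4 repeats this. The synopsis has nearly the same definition: "Grade 3 or 4 non-hematologic toxicity that does not resolve to baseline in 28 days with standard of care", again with Grade 4 as the hematologic threshold.
- **Unacceptable toxicity.** Protocol 2.2 gives the trigger as "completion of the planned 12 cycles or unacceptable FOLFOX related toxicity". Section 5.1.1, SAP 6.3 and another paragraph of the synopsis use the same idea. None gives a grade or duration, and none refers to 2.2.1.
- **Toxicity without a qualifier.** Section 6.3.1, which sets the maintenance procedures, describes the move to AM0010 alone thus: "after completion of up to 12 planned cycles of FOLFOX or discontinuation of FOLFOX due to toxicity, patients assigned to ARM 1 may continue".

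Section 5.1.3 uses the term chemotherapy intolerance without defining it. Section 4.1 lists reasons for stopping any study drug, patient request among them, and then says: "In addition, the patient should continue with the rest of the treatment regimen and the study-related procedures per the protocol". It does not mention maintenance.

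The maintenance dose also has two versions. The text of 2.2, 5.1.1 and 6.3.1 gives 0.8 mg (80 kg or less) or 1.6 mg (over 80 kg). The notes to the Arm 1 figures in the synopsis, 2.2 and 5.1.3 give 0.4 mg or 0.8 mg.

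**The concern.** Entry to maintenance decides which AM0010 dose applies and from what date. If one site works from 2.2.1 and another from 6.3.1, the same clinical course can lead to different Arm 1 treatment, with both sites following the protocol.

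The SAP inherits the ambiguity. Section 8.1 counts patients who went on to maintenance. Section 10.1.1 splits cumulative dose, dose per cycle and relative dose intensity at the start of maintenance, yet describes maintenance only as what follows cycle 12. An early entrant has no clear place in that split.

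**Working it through.** **1. Patients on whom the wordings differ.** Take an Arm 1 patient without progression whose FOLFOX is stopped before cycle 12.

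| Reason FOLFOX stopped | 28-day definition (synopsis, 2.2.1, SAP 6.4) | Unacceptable toxicity (synopsis, 2.2, 5.1.1, SAP 6.3) | 6.3.1 |
|---|---|---|---|
| Grade 4 hematologic, unresolved at day 28 | Qualifies | If judged unacceptable | Qualifies |
| Grade 3 hematologic, any duration | Does not | If judged unacceptable | Qualifies |
| Grade 3 non-hematologic, resolved before day 28 | Does not | If judged unacceptable | Qualifies |
| Grade 2 toxicity | Does not | If judged unacceptable | Qualifies |
| Patient request, no toxicity | Not named | Not named | Not named |

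Rows two to four are the contradiction. The last row is a gap: 4.1 keeps the patient on the rest of the regimen, but the 5 µg/kg dose is stated for use while FOLFOX is being given, and the 10 µg/kg dose for completion or toxicity. Neither covers this patient.

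The first row has its own difficulty when the toxicity is thrombocytopenia. Section 5.2 holds AM0010 as well as FOLFOX until platelets recover. Section 5.3 uses 28 days without therapy as a trigger for discontinuing AM0010 and/or FOLFOX, with an exception for clinical benefit plus approval. Section 2.2.1 at the same point opens maintenance.

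**2. The plan's planned amounts.** There are 10 dosing days per 14 (Days 1–5 and 8–12).

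- Combination: 0.4 × 10 = 4 mg; 0.8 × 10 = 8 mg.
- Maintenance, text doses: 0.8 × 10 = 8 mg; 1.6 × 10 = 16 mg.

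These reproduce SAP 10.1.1, and the ratio is 2. With the figure-note doses, maintenance is 0.4 × 10 = 4 mg or 0.8 × 10 = 8 mg, and the ratio is 1.

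**3. Patients already on a reduced AM0010 schedule.** Section 5.2 reduces AM0010 by dosing days: 4 per week (80%) or 3 per week (60%). Section 6.3.1 gives maintenance as 5 days on and 2 off, with the same two reduction steps available, but does not say whether an existing reduction carries over. Weekly amounts at 80 kg or less:

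| Schedule before entry | mg/week before | Text dose, reset to 5 days | Text dose, reduction kept | Figure-note dose, reset | Figure-note dose, kept |
|---|---|---|---|---|---|
| 80% | 4 × 0.4 = 1.6 | 4.0 (2.5-fold) | 3.2 (2-fold) | 2.0 (1.25-fold) | 1.6 (1-fold) |
| 60% | 3 × 0.4 = 1.2 | 4.0 (3.3-fold) | 2.4 (2-fold) | 2.0 (1.7-fold) | 1.2 (1-fold) |

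The ratios are the same above 80 kg, since every dose doubles. The step at entry therefore runs from none to 3.3-fold, depending on two points the text leaves open.

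**4. Effect on relative dose intensity.** A patient of 80 kg or less receiving 8 mg per 2 weeks scores 8/4 = 200% if the period is classed as before maintenance and 8/8 = 100% if it is classed as maintenance.

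**The case against.** The best defence is that the unacceptable-toxicity wording is shorthand for the definition in 2.2.1. The synopsis contains both wordings, and SAP 6.3 and 6.4 sit next to each other, which is compatible with interchangeable use. That could reconcile 2.2, 5.1.1 and SAP 6.3, although no cross-reference says so. It does not reconcile 6.3.1, which has no qualifier to read as shorthand.

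It is also fair that the disputed cases need an investigator's decision. For Grade 3–4 anemia or thrombocytopenia, Table 11 prescribes hold and reintroduce at every listed occurrence, not a FOLFOX stop. But 4.1 lists adverse events and investigator decision among the reasons for discontinuation, so the cases can arise. The documents do not show how often.

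Some stronger readings are not supported:

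- A reader might infer from 4.1, or from the Appendix A maintenance column, that FOLFOX may be stopped for any reason and maintenance begun. Section 4.1 never mentions maintenance, the Appendix A entry is only a visit heading, and 6.3.1 ties maintenance to completion or toxicity.
- A reader might infer that AM0010 must stop when the 28-day definition is not met. Section 2.2.1 is permissive, and the synopsis lets patients with toxicity due to one drug continue the others on the investigator's judgement.
- A reader might infer that the rules start maintenance at least 28 days apart. If FOLFOX itself ends through the 28-day delay rule in 5.3, entry could fall at about the same time under either.
- The 55% rate of Grade 3–4 thrombocytopenia comes from uninterrupted daily AM0010 with FOLFOX, and counts recovered within 7 days of interruption. It does not estimate how often FOLFOX will be stopped early.

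**Conclusion.** The inconsistency is real. The synopsis, 2.2.1 and SAP 6.4 contain a graded 28-day definition that 6.3.1 does not apply. At least two kinds of patient, those stopped for Grade 3 hematologic toxicity and those stopped for Grade 3 non-hematologic toxicity resolved before day 28, are classified in opposite ways. Two gaps go with it: the AM0010 dose after a non-toxicity FOLFOX stop, and whether an earlier schedule reduction carries into maintenance.

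The size per patient is a doubling of planned AM0010 on SAP 10.1.1's figures, or no increase on the figure-note doses. The 3.3-fold step applies only if the text dose holds and a patient at 60% is reset to five days a week. The number of patients affected cannot be derived from the documents.

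The consequence is variable Arm 1 treatment and maintenance exposure summaries that mix differently defined entrants. The primary comparison is by randomized arm, so the ITT overall survival test and the 393-event requirement are unchanged; any effect on survival would come only through the treatment received. These are contradictory operative rules and should be corrected. This is not an error in the primary analysis, and nothing here says which rule or dose is right.

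**What to change.** Reconcile the synopsis, protocol 2.2, 2.2.1, 4.1, 5.1.1, 5.1.3, 5.3 and 6.3.1, and SAP 6.3, 6.4 and 10.1.1, to a single definition of entry to maintenance, stated once and cross-referenced elsewhere. The same text should cover:

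- what happens to AM0010 when FOLFOX stops for a reason other than toxicity;
- whether an existing AM0010 schedule reduction carries over;
- one maintenance dose, so that the figure notes and the text agree.

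The sponsor chooses the rule and the dose. In SAP 10.1.1, define the start of maintenance so that early entrants are placed in the exposure split. Counting entries by route (cycles completed, toxicity, other) in the SAP 8.1 disposition table would help but is optional.

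The cost is a protocol clarification and a matching SAP edit, plus a few table rows if the counts by route are added. Sample size, event count and the primary test do not change.

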2.2.2 Evaluation of Molecular Biomarkers

2.2.2.1 Carbohydrate CA 19-9

Serum levels of CA 19-9 will be evaluated over time to assess changes after treatment with AM0010 plus FOLFOX and FOLFOX alone. Since CA 19-9 is being used only in an exploratory evaluation to determine whether there is a correlation with efficacy outcomes, increases in CA 19-9 levels in this study should not be used as evidence for progressive disease or for removing patients from study treatments.

2.2.2.2 Other Exploratory Molecular Markers

The following additional optional biomarkers may be quantified and correlated with subsequent anti-tumor responses: i) Pre-treatment intratumoral CD8+ T cells and MHC I expression levels in archival tumor samples may be quantified to determine if a pre-treatment intratumoral immune signature effects AM0010 treatment outcomes; ii) Treatment-associated changes in the serum biomarkers IL-18, IFN γ , IL-4, and transforming growth factor-beta (TGF β) may be quantified to assess both the duration of AM0010 mediated immune activation and whether there is an AM0010 serum immune signature that correlates with PR/CR anti-tumor responses; and iii) Peripheral blood T-cell receptor (TCR) β sequences and PBMC and mRNA may be obtained from on-treatment serial blood draws.

2.2.3 Number of Study Sites

This study will be conducted at approximately 150 sites in North America, Europe, and Asia-Pacific.

2.2.4 Number of Patients

The study will randomize approximately 566 patients.

2.2.5 Study Completion Definition

This study will be considered complete (ie, the scientific evaluation will be complete) once it has been determined by Lilly that the evaluation of primary and secondary objectives is sufficient and complete. Investigators will continue to follow the study schedule for all patients until notified by Lilly that study completion has occurred. After study completion, the patients who are on treatment

and continuing to receive clinical benefit may continue receiving study drugs during the continued-access period.

2.2.6 Continued-Access Period

All patients remaining on study treatment without disease progression following study completion will enter the continued-access period of the study. The continued-access period begins after study completion and ends at the end of trial. During the continued-access period, patients on study treatment who continue to experience clinical benefit may continue to receive study treatment until disease progression, death, unacceptable toxicity, or end of trial. Patients who are in the 30-day follow-up, but have not yet completed the visit will complete the necessary follow-up visit when the continued-access period begins and then discontinue the study. If it is deemed to be in the best interest of the patient to start a new anti-cancer treatment prior to a scheduled follow-up visit, the follow-up visit duration may be shortened. In this case, the follow-up assessments should be completed prior to the initiation of the new therapy.

Lilly will notify investigators when the continued-access period begins.

During the continued-access period, all relevant assessments will be done according to [Appendix B](#) and recorded on the case report form (CRF).

Serious adverse events (SAEs) will also be reported to Lilly Global Patient Safety and collected in the pharmacovigilance system. In the event that an SAE occurs, additional information (such as local laboratory results, concomitant medications, and hospitalizations) may be requested by Lilly in order to evaluate the reported SAE.

Investigators may perform other standard procedures and tests needed to treat and evaluate patients; however, Lilly will not routinely collect the results of these assessments.

